ISIS 420915-CS2 is a Phase 2/3 multicenter, double-blind, placebo-controlled study to assess the efficacy and safety of ISIS 420915 in patients with FAP. The study plans to enroll approximately 135 patients randomized 2:1 (ISIS 420915 to placebo) to receive 300 mg ISIS 420915 or placebo. The Study Drug is administered 3 times during the Week 1 and once weekly during Weeks 2 to 65.

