3.2.2 Patient Populations Analyzed

The following analysis populations are defined for this present OLE study:

- Screened patients will be defined as patients who signed an informed consent form.
- Enrolled patients will be defined as patients who signed an informed consent form and were not screen failures.
- The FAS will include all enrolled patients who received at least 1 injection of ISIS420915 in the
 OLE study and who have at least one post-baseline efficacy assessment for the mNIS+7 score or
 Norfolk QOL-DN questionnaire total score collected after CS3 Study Day 1 in this OLE study. This
 will be the primary population for analysis of efficacy and PD outcomes.
- The Safety Set (SS) will include all enrolled patients who received at least 1 injection of ISIS
 420915 in the OLE study. This population will beused for analyses of all safety measures
 collected in this OLE study. Results will be summarized under the treatment which the patients
 received in the parent study.
- The Longitudinal Safety Set (LSS): will include all patients who received at least 1 injection of ISIS 420915 in the parent study. This population will beused for the longitudinal safety analysis for either the parent study or this OLE study. Results will besummarized under the treatment which the patients received in the parent study. Note that this population will include patients who receive ISIS 420915 in the parent study but did not enter this OLE. It does not include patients who took placebo in CS2.
- The PPS will include the subset of the Full Analysis Set that have received at least 70% of the prescribed doses of ISIS 420915 in this OLE study and that have no significant protocol deviations in the OLE study that would be expected to affect efficacy assessments. Prescribed doses of ISIS420915 mentioned above is defined as the total assigned dose in mg from the Week 1 to the last dose within this study up to week 156 (first three years), i.e. 300mg*156 doses= 46800mg. Patients in FAS of this OLE study but excluded from PPS in the parent study will be excluded from the PPS in this OLE study as well. This will be a secondary population for

efficacy and PD analyses. The detailed criteria and definitions for major protocol violations will be specified. Results will be summarized under the treatment which the patients received in the parent study.

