3.3.2 Adverse Events (AEs)

Adverse events will be coded using Medical Dictionary for Regulatory Activities (MedDRA). The final version used will be designated in the clinical study report. For each AE, the severity level of the event (mild, moderate, or severe) will be determined by physician opinion.

TEAEs are defined as adverse events that first occurred or worsened after the first dose of Study Drug (ISIS 420915 or Placebo). This is the general definition of TEAEs. A detailed definition of TEAEs for safety analysis of the OLE study or for the longitudinal safety analysis will be discussed in section 3.3.2.6 or in section 3.3.2.7, respectively.

In this section, whenever first dose of ISIS 420915 is used, it refers to **CS3 Study Day 1** for OLE study analysis and **Day 1 of ISIS 420915** for longitudinal safety analysis.

An AE with a completely missing start date will be assumed to be treatment emergent.

If the maximum severity of the adverse event is greater than the baseline severity, i.e. severity prior to the first dose of ISIS 420915, or if the onset date/time is the same as or after the date/time of the first dose of ISIS 420915, then the event is considered to be treatment emergent.

In the situation where change in severity (but no change in seriousness) occurs for an adverse event, study sites are instructed to enter an end date and start a new record for the adverse event. In the new record, the changed severity is to be recorded and the start date will be set to be the end date of the previous record. Data linking those records are collected in the database. Consider three scenarios:

- The first AE record occurs prior to the first dose of ISIS 420915, the second AE record occurs on
 or after the first dose of ISIS 420915, and the severity increases: Only the second record will be
 counted as treatment-emergent.
- The first AE record occurs prior to the first dose of ISIS 420915, the second AE record occurs on or after the first dose of ISIS 420915, and the severity decreases: Neither record will be counted as treatment-emergent.
- Both records occur on or after the first dose of ISIS 420915: If the AE severity on the second record is worse than the severity on the first record, then count both records as treatmentemergent. But, if the severity improves, then only count the first record as treatmentemergent.

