3.3.2.6 OLE Study Analysis of TEAEs

TEAEs which occur during the OLE study include TEAEs which first occurred or worsened on or after **CS3 Study Day 1**. Derivation is described in Section 3.3.2.

The following categories of AEs in the OLE study will be summarized by treatment group from the parent study: all TEAEs; TEAEs leading to early discontinuation from Study Drug or from the study; and serious adverse events. The percentage of patients reporting the adverse event will be summarized by MedDRA System Organ Class (SOC) and Preferred Term (PT), and will be sorted by SOC alphabetically and then by decreasing frequency of PT within SOC.

Summaries of drug related TEAEs, TEAEs by maximum severity, TEAEs grouped by duration of exposure to the Study Drug at the start of the event (< 6 months, \geq 6 months to < 12 months, \geq 12 months to < 24 months, \geq 24 months to < 36 months, \geq 36 months to < 48 months, \geq 48 months to < 60, \geq 60 months) and Number of dose at the start of event (<26, \geq 26 to < 52, \geq 52 to < 104, \geq 104 to < 156, \geq 156 to < 208, \geq 208 to 260, \geq 260) will also be provided. Duration of exposure and the number of doses is calculated from **CS3 Study Day 1** to the start date of event.

All TEAEs will be summarized for subgroups defined by the following variables:

- Age at parent study screening (<65 years and >=65 years),
- Sex (Female and Male),
- Race (White, non-White),
- Region (North America, Europe and South America / Australasia),
- CM-ECHO Set (Included and Not Included).

As well as stratification factors at randomization during the parent study, including

- V30M TTR mutation (Yes, No),
- previous treatment with Vyndagel® or Diflunisal (Yes, No),
- Disease stage (Stage 1 and Stage 2).

Results will not be provided for a variable if the overwhelming majority of patients are within one level of the subgroup. Non-TEAEs reported will be flagged in the all AE listing.

TEAEs in the following categories will also be summarized in tables and listed separately:

- Adverse events of special interest (defined in section 3.3.2.1)
- Other adverse events of interest (defined in section 3.3.2.2)
- Local cutaneous reactions at injection site (defined in section 3.3.2.3)
- Flu-like reactions (defined in section 3.3.2.4)

Summary tables of the number and percentage of patients with these adverse events will be displayed split by AE category and treatment group received in the parent study.

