3.3.2.7 Longitudinal Safety Analysis of TEAEs

For this summary TEAEs are defined as those events which first occurred or worsened on or after first dose of ISIS in the parent study.

Adverse events summaries including data from the combined study periods of the parent and OLE studies will be provided for subjects in the LSS analysis population. These summaries will include all TEAEs which started on or after the first dose of ISIS 420915 in the parent study and before the day of the patient's last contact date. For subjects who enrolled in the OLE study, the last contact date would be the one obtained from the OLE study. For subjects who are not enrolled in the OLE study the last contact date would be the one obtained from the parent study. Note that AEs which started during the gap period between the completion of the parent study and the first dose of the OLE study and are not considered TEAEs in the OLE study will still be included in these summaries. In other words, it is possible that there will be events which are not considered parent study TEAEs or OLE study TEAEs, but will be counted towards this analysis.

These TEAEs will be summarized for subgroups defined by the following variables: Age at parent study screening (<65 years and >=65 years), Sex (Female and Male), Race, Region (North America, Europe and South America /Australasia), and CM-ECHO Set (Included and Not Included). Results will not be provided for a variable if the overwhelming majority of patients are within one level of the subgroup.

Summaries of drug related TEAEs, TEAEs by maximum severity, adverse events leading to early withdrawal from Study Drug, TEAEs duration of exposure to Study Drug at the start of event (< 6 months, \geq 6 months to < 12 months, \geq 12 months to < 24 months, \geq 24 months to < 36 months, \geq 36 months to < 48 months, \geq 48 months to < 60 months, and \geq 60 months)and Number of doses at the start of event (26, \geq 26 to < 52, \geq 52 to < 65, \geq 65 to < 104, \geq 104 to < 156, \geq 156 to < 208, \geq 208 to < 260, \geq 260) will also be provided. Duration of exposure and the number of doses is calculated from **Day 1 of ISIS 420915** to the start date of event.

TEAEs in the following categories will also be summarized in tables and listed separately:

- Adverse events of special interest (defined in section 3.3.2.1)
- Other adverse events of interest (defined in section 3.3.2.2)

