Time from **CS3 Study Day 1** to the onset of each of these events collected in the OLE study will be summarized for the patients in SS that met the criterion. Summaries including the following descriptive statistics: mean, standard deviation, median, P25, P75, and minimum and maximum.

Kaplan-Meier plots for time to first event will also be provided for value < 140×10^9 /L, value < 100×10^9 /L and value < 75×10^9 /L.

The post-baseline nadir (absolute value, change from the **ISIS 420915 baseline**, and percent change from the **ISIS 420915 baseline**) of platelet count will be summarized by treatment group of the parent study.

Duration of platelet counts below the $140 \times 10^9/L$ will be summarized, based on the duration (in weeks) each patient was below the $140 \times 10^9/L$.

The above analyses will be repeated for the subgroups defined by CM-ECHO Set.

Scatter plots for nadir platlets versus the **ISIS 420915 baseline** of BMI, mBMI, and weight will be provided.

A listing of patients with dose pause due to Platelet < 75 x10^9/L will also be provided.

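### SAP 3.3.4.2 times platelet events in the extension from CS3 Study Day 1 without setting aside patients who already meet the criterion at entry, so declines carried over from CS2 count as new onsets

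*Combined protocol and SAP*

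**What the plan says.** **Platelets.** SAP 3.3.4.2 lists graded counts, absolute limits and confirmed decreases of at least 30% and 50% from the ISIS 420915 baseline. For Safety Set patients who meet a criterion, it summarises the time from CS3 Study Day 1 to onset. It adds: "Kaplan-Meier plots for time to first event will also be provided for value", followed by the limits below 140, below 100 and below 75 × 10^9/L. No sentence in that section removes a patient who already meets the criterion at entry.

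**Baseline.** Under SAP 3.2.1.1.2, the ISIS 420915 baseline is the parent-study baseline for patients randomised to active drug in CS2 and the OLE study baseline for those randomised to placebo.

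**Longitudinal version.** SAP 3.3.4.4 repeats the platelet analyses on the Longitudinal Safety Set (LSS), with time running from Day 1 of ISIS 420915. Of that set, SAP 3.2.2 says: "It does not include patients who took placebo in CS2".

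**Adverse-event exposure tables.** SAP 3.3.2.6 summarises "TEAEs grouped by duration of exposure to the Study Drug at the start of the event", and number of doses likewise, and states: "Duration of exposure and the number of doses is calculated from CS3 Study Day 1 to the start date of event". In SAP 3.3.2.7 the matching LSS quantity "is calculated from Day 1 of ISIS 420915 to the start date of event". SAP 3.3.2 gives the general rule for first dose: "it refers to CS3 Study Day 1 for OLE study analysis and Day 1 of ISIS 420915 for longitudinal safety analysis".

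**The concern.** The primary objective is the safety of extended dosing, and platelet decline is one of the adverse events of special interest. A time-to-onset summary or Kaplan-Meier curve is read as showing when patients who were free of the event first develop it. If some patients enter with the event already present, the first part of the curve shows prevalence at entry, not onset during the extension.

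The effect is uneven between the parent-study groups. Former-active patients enter after up to 65 weeks on drug, and their percentage change is still measured from before CS2. Former-placebo patients start both drug and baseline at CS3 Study Day 1. Persisting CS2 declines in the first group would sit beside genuine first-exposure onsets in the second, at the same early time points and under the same label.

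**Working it through.** **1. Prior exposure, reproducing the plan's figure.** Protocol 2.4 gives 65 weeks (15 months) in CS2 and 325 weeks in all. Check: 65 × 7 / 30.4375 = 14.95 months, and 65 + 260 = 325 weeks. Doses in CS2: "The Study Drug is administered 3 times during the Week 1 and once weekly during Weeks 2 to 65", so 3 + 64 = 67.

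**2. Can a criterion be met at entry?** Let B be the ISIS 420915 baseline and X the last platelet count before CS3 Study Day 1.
- Former-placebo: B is the OLE study baseline, defined as that same last value, so the decrease at entry is (B − X)/B = 0. A percentage criterion cannot already be met, though an absolute limit can.
- Former-active: B is the CS2 baseline, so (B − X)/B can take any value. Both percentage and absolute criteria can already be met.
- Eligibility (protocol 5.1 and 5.2) sets no platelet minimum; it relies on judgement about tolerability and new or worsening conditions.

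The percentage and absolute criteria pick out different patients. A 30% fall leaves a count of at least 140 when B ≥ 140/0.70 = 200, and a 50% fall does so when B ≥ 140/0.50 = 280 (× 10^9/L). A former-active patient can thus meet a percentage criterion at entry with a count at or above the lower limit of normal, so the check must be made criterion by criterion.

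**3. When would the carried-over event be recorded?** The first platelet window in SAP Appendix 3 is Week 2, target Day 8 (Days 7 to 11). Under SAP 3.3.4 a value is confirmed by a same-or-worse consecutive result on a different day within 7 days, and presumed confirmed if there is no retest. A persisting low count therefore passes the confirmation rule. SAP 3.2.1.4 also admits post-baseline data from CS3 Study Day 1. For a former-active patient the Day 1 draw is already later than the CS2 baseline, and the text does not say whether it counts.

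**4. Effect on the curve.** Let p be the share of a displayed group already meeting the criterion, and F(t) the true cumulative incidence among the rest. If all carried-over cases still meet it at the first draw, the planned curve shows

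p + (1 − p) F(t),

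an excess over F(t) of p (1 − F(t)). The excess is p at the first draws and shrinks as F(t) rises. The time-to-onset summaries include only patients with the event, so carried-over cases near Day 8 pull their mean and quartiles down.

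**5. Size.** The planned split is 90 active and 45 placebo (SAP 1.1), so 90/135 = 67% of patients are former-active if all enter. The documents give no p. Purely as assumptions, p = 10% would be 0.10 × 90 = 9 patients and p = 20% would be 18; p = 0 means no distortion.

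**6. The wording point.** An event at OLE month 3 in a fully treated former-active patient has cumulative exposure of about 3 + 14.95 = 17.95 months, ignoring any gap between studies. It appears under <6 months in 3.3.2.6 and under 12 to <24 months in 3.3.2.7, and the row description in 3.3.2.6 does not itself say which clock applies.

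**The case against.** The strongest defence is that the extension clock is declared and is not the only one. SAP 3.3.4.2 refers to events collected in the OLE study, and 3.3.4.4 supplies the version from first active dose for every patient treated with active drug in CS2. For former-placebo patients CS3 Study Day 1 is the first active dose. The platelet shift tables show the baseline category, the study has no formal hypotheses, and nothing shows that many patients entered with low counts. At the lowest plotted limit, carry-over is less plausible: protocol 8.6.3 holds dosing after a confirmed count below 75,000/mm³ until at least 100,000/mm³.

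This limits the likely size but does not remove the problem. The LSS output is a separate display; the Safety Set plots still present a first event without a clean risk set. The shift tables use the CS2 baseline for former-active patients, so they do not show status at OLE entry. The Day-90 interim (SAP 5.2) omits the longitudinal set.

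A reader might go further on the exposure tables in 3.3.2.6 and infer that every former-active event is misfiled and that first-exposure and later events are mixed. The documents do not support that:
- The clock is defined in 3.3.2 and again in 3.3.2.6. With 30.4375-day months, no on-treatment OLE day (to Day 1814 + 7 = 1821) shares a band under both clocks for a fully treated former-active patient, but that measures the distance between two defined clocks, not an error rate. Events at ≥60 months or ≥260 doses keep their band under either.
- SAP 3.2.1 and protocol 10.6.2 lay the tables out by parent-study group, so the two kinds of event share row labels but sit in separate columns. The exposure sentence does not repeat this, so the reading rests on the general convention.
- SAP 3.3.2.7 gives cumulative exposure for exactly the affected patients.

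Nor would it help to start former-active Safety Set patients at Day 1 of ISIS 420915. OLE events count only from CS3 Study Day 1, so their early exposure rows would be empty by construction, and their Kaplan-Meier curves would gain about 15 event-free months.

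**Conclusion.** The platelet point holds. Followed as written, SAP 3.3.4.2 counts low platelets or declines persisting from CS2 as new events at the first OLE draws. For percentage decreases this can happen only in former-active patients; for absolute limits it can happen in either group. The excess in a curve is p(1 − F(t)), largest at the start. It rests on the condition persisting to the first draw and on p, which the documents do not give, so the actual size is unknown.

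For the adverse-event tables only a labelling point remains, and it matters most at the Day-90 interim, where no cumulative table is produced.

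**What to change.** **Main change, SAP 3.3.4.2.** For the Safety Set time-to-onset summaries and Kaplan-Meier plots, define the risk set separately for each criterion as patients who do not meet it at their last platelet value on or before CS3 Study Day 1. Report the number already meeting it, by parent-study treatment group, next to each summary or curve. State how confirmed criteria and missing entry values are handled when setting this flag. Keep the LSS version in 3.3.4.4 for time since first exposure.

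**Wording, SAP 3.3.2.6.** Title the tables as duration of exposure and number of doses in the OLE, counted from CS3 Study Day 1; state that they are shown by parent-study treatment group; and cross-refer to the cumulative table in 3.3.2.7.

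**Cost.** One entry-status flag per platelet criterion from data already collected, a re-run of the onset summaries and three plots, and revised titles. The downside is somewhat fewer patients in each Safety Set curve.

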3.3.2.7 Longitudinal Safety Analysis of TEAEs

For this summary TEAEs are defined as those events which first occurred or worsened on or after first dose of ISIS in the parent study.

Adverse events summaries including data from the combined study periods of the parent and OLE studies will be provided for subjects in the LSS analysis population. These summaries will include all TEAEs which started on or after the first dose of ISIS 420915 in the parent study and before the day of the patient's last contact date. For subjects who enrolled in the OLE study, the last contact date would be the one obtained from the OLE study. For subjects who are not enrolled in the OLE study the last contact date would be the one obtained from the parent study. Note that AEs which started during the gap period between the completion of the parent study and the first dose of the OLE study and are not considered TEAEs in the OLE study will still be included in these summaries. In other words, it is possible that there will be events which are not considered parent study TEAEs or OLE study TEAEs, but will be counted towards this analysis.

These TEAEs will be summarized for subgroups defined by the following variables: Age at parent study screening (<65 years and >=65 years), Sex (Female and Male), Race, Region (North America, Europe and South America /Australasia), and CM-ECHO Set (Included and Not Included). Results will not be provided for a variable if the overwhelming majority of patients are within one level of the subgroup.

Summaries of drug related TEAEs, TEAEs by maximum severity, adverse events leading to early withdrawal from Study Drug, TEAEs duration of exposure to Study Drug at the start of event (< 6 months, \geq 6 months to < 12 months, \geq 12 months to < 24 months, \geq 24 months to < 36 months, \geq 36 months to < 48 months, \geq 48 months to < 60 months, and \geq 60 months)and Number of doses at the start of event (26, \geq 26 to < 52, \geq 52 to < 65, \geq 65 to < 104, \geq 104 to < 156, \geq 156 to < 208, \geq 208 to < 260, \geq 260) will also be provided. Duration of exposure and the number of doses is calculated from **Day 1 of ISIS 420915** to the start date of event.

TEAEs in the following categories will also be summarized in tables and listed separately:

- Adverse events of special interest (defined in section 3.3.2.1)
- Other adverse events of interest (defined in section 3.3.2.2)
- Local cutaneous reactions at injection site (defined in section 3.3.2.3)
- Flu-like reactions (defined in section 3.3.2.4)

Summary tables of the number and percentage of patients with these adverse events will be displayed split by AE category.

Mortality defined in section 3.3.2.5 on LSS will be summarized.

